For the analysis of rates of relapse, we will examine time to relapse as rated by the MINI during pregnancy and across the 6-month postpartum follow up using survival analysis. Survival rates will be compared using Cox proportional hazard regression and illustrated in Kaplan-Meier curves (Collett, 1994). However, time to attrition is a competing risk that can be related to time to relapse. We will adopt the subdistribution hazard model (SHM) developed by Fine and Gray to account for the possible non-independence of the censoring mechanism.²⁵

For the continuous outcomes, we will use Hierarchical Linear Models (HLM) as our primary analytic model, which will compare change over time between groups on depressive symptom burden using the PHQ-9. HLM is flexible with respect to the nature of change over time (i.e., linear, piecewise linear, loglinear, etc.), and will accommodate the within subject correlation through the inclusion of random effects at the patient-level, accounting for the patient-to-patient deviations. Pattern-mixture models²⁶ will be used to assess whether important estimates (i.e., intervention effects) are dependent on missing data and to provide overall estimates of effects by averaging over the various missing-data patterns.

Analysis for Specific Aim #2: To explore the specific benefit of MMB relative to AD discontinuation and questions regarding personalization that are of strong interest to pregnant women and their healthcare providers.

H2a: Comparison of MMB to UC among women who discontinue AD: Our analysis will be the same as H1 with both the time-to relapse and continuous outcome models. We predict that rates of relapse and symptom burden among women randomized to MMB who discontinue AD will be significantly superior to those randomized to UC who discontinue AD.

H2b: Treatment Selection Algorithm: We predict that the use of a treatment selection algorithm will differentiate two profiles of women based on pre-treatment characteristics (those who are optimally suited to discontinue AD and engage MMB to minimize their risk of relapse, and those who should continue AD to minimize risk of relapse) and that women who are randomized to the algorithm indicated approach will have significantly lower risk of relapse and symptom burden than women who are randomized to their algorithm contraindicated approach.

Analysis for Specific Aim #3: To test the extent to which digital MMB engages putative targets.

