H2b: Treatment Selection Algorithm: Although there has been growing interest in trials focused on estimation of an optimal personalized treatment strategy,³⁵ there are no standard formula since the outcome of interest, the personalized treatment regimen, is not a measurable outcome as in typical power derivations.³⁶ Laber and colleagues provide a method for sizing such a trial, which they apply to their fertility (time to pregnancy) data example.³⁷ In their setting, they estimated a sample size of 280 was needed to yield 80% power for superior coverage with 9 terms (including main effects and interaction terms) with an interval width of 0.38. Based on a slight modification of width to 0.40, we estimate a sample size of 250 is needed with 9 terms. Based on our prior data,¹⁰ we project that 50% of participants randomized to MMB will discontinue AD (n=150) and 50% of participants randomized to UC will continue AD (n=150); thus, our randomized sample (N=600) should be sufficiently powered to build a model with up to 4 moderator variables (the number identified in our preliminary data). We will conduct PAI analysis with the SAS software procedure PROC QLEARN.

Power Analysis for Specific Aim #3: To test the extent to which digital MMB engages putative targets. Fritz et al. derived sample size requirements to guarantee 80% power.³⁸ With a small to medium effect for treatment on the mediator and a small to medium effect for treatment on outcome, covarying the mediator, the sample size for 80% power is 224 patients; therefore, our proposed sample, even with as much as 30% attrition is more than sufficient to test mediation with 80% power.

VII.. RISKS AND DISCOMFORTS

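### H2b's sample size of 250 is a width rescaled from a fertility example: it gives no power for the indicated-versus-contraindicated comparison, and the plan's own 30% attrition leaves 210 women

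*Combined protocol and SAP*

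**What the plan says.** All references are to section VI, Biostatistical Analysis, of the combined protocol and SAP unless stated.

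- **Hypothesis.** The analysis text for Aim 2, H2b predicts that "women who are randomized to the algorithm indicated approach will have significantly lower risk of relapse and symptom burden" than women on the contraindicated approach. Hypothesis 2b in section II makes the same prediction in terms of superior outcomes. The preliminary-analyses paragraph sets significance at p < .05.
- **Source of the sample size.** The Aim 2 power text for H2b cites a published method, "which they apply to their fertility (time to pregnancy) data example". It reports: "In their setting, they estimated a sample size of 280 was needed to yield 80% power for superior coverage with 9 terms", "with an interval width of 0.38".
- **Adaptation.** "Based on a slight modification of width to 0.40, we estimate a sample size of 250 is needed with 9 terms". No reason is given for choosing 0.40, and the scale of the width is not stated.
- **Conclusion.** The plan projects 150 MMB women who discontinue AD and 150 UC women who continue it. It concludes that the randomised sample "should be sufficiently powered to build a model with up to 4 moderator variables".
- **Attrition.** The power paragraphs for Aim 1, H2a and Aim 3 each allow 30%. The H2b paragraph allows none.

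**The concern.** H2b ends in a significance claim about relapse and symptom burden, but its sample size comes from a precision criterion for a different outcome in a different study. H2a, in the paragraph before, gives a difference (23%), a power (82.8%) and an attrition allowance. H2b gives none of these for the comparison it will report.

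H2b is meant to distinguish women suited to discontinuing AD with MMB from women suited to continuing AD. Whichever way the result falls, a reader needs to know what size of separation the trial could have detected. The plan does not say, and its reassurance rests on a head count (300 against 250) that omits its own attrition rate.

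**Working it through.** **1. Reproduce the 250.** Inputs from the H2b power paragraph: N = 280 at width 0.38, new width 0.40. Interval width scales with 1/√N, so

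N = 280 × (0.38/0.40)² = 280 × 0.9025 = 252.7,

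which matches the printed 250 to about 1%. Linear scaling gives 280 × 0.38/0.40 = 266 and does not match. The nine terms fit four moderators: 1 treatment + 4 main effects + 4 interactions. The arithmetic is sound, but every input belongs to the borrowed example.

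**2. Apply the plan's attrition.**

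- Available: 150 + 150 = 300. Less 30%: 300 × 0.70 = 210, which is below 250.
- Width at 210 on the same scaling: 0.38 × √(280/210) = 0.44, not 0.40.
- Women needed in the two cells to leave 250 analysable: 250/0.70 = 357.1, or 358 with equal cells.

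**3. A further possible loss.** The UPWARD Extension text in section V says the final 100 of the 600 women have no follow-up clinical interviews or relapse determination calls. The Extension measurement schedule nevertheless marks the MINI mood module at three follow-up visits. The two must be reconciled. If the text is right and these women fall evenly across the cells, the two H2b cells hold 500/2 = 250 women with relapse interviews, or 250 × 0.70 = 175 after attrition.

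**4. What the H2b comparison could detect.** The plan gives no relapse rates or split for the indicated and contraindicated groups, so these are assumptions: relapse averaging 45%, equal groups of n, binary relapse, two-sided 5%. If the rule were known in advance, with difference d and p₁, p₂ = 0.45 ± d/2,

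power ≈ Φ[(d − 1.96·s₀)/s₁], where s₀ = √(2 × 0.45 × 0.55/n) and s₁ = √((p₁(1−p₁) + p₂(1−p₂))/n).

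For 210 women, n = 105 and s₀ = 0.0687. At d = 0.20, s₁ = 0.0673 and power = Φ[(0.20 − 0.1346)/0.0673] = Φ(0.97) ≈ 84%.

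In practice the rule must be estimated. The second and third rows below come from simulation: two equal cells, four normal moderators (one or all four truly moderating), a linear nine-term model, 10-fold cross-validated recommendations, and a pooled two-proportion test. Repeat runs move these figures by a few points.

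| Setting | 10 points | 15 points | 20 points |
|---|---|---|---|
| Rule known, 210 women | 31% | 59% | 84% |
| Rule cross-validated, 210 women | about 20% | about 41% | about 70% |
| Rule cross-validated, 300 women | 26–31% | 58–59% | 85–86% |

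With the rule known and contraindicated relapse varied from 30% to 60%, the smallest difference detectable with 80% power is 16–19 points at 210 women and 14–16 points at 300.

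**5. Calibration.** With no true moderation, the two-sided cross-validated test rejects in about 11–15% of runs (4–6% in the favourable direction). The recommendations in each fold depend on outcomes in the others, so the nominal 5% does not hold. The cross-validated figures, above all at 10 points, are therefore illustrative.

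**The case against.** The plan is candid. It concedes that no accepted formula exists for this kind of outcome, names the fertility example, attributes the 80% to that example's setting, and calls its change of width slight. Aim 2 is worded as exploratory. The conclusion claims only enough power to build a model; it does not say that 250 women power the indicated-versus-contraindicated test. All of this stands, and it keeps the severity modest. It does not supply a power statement for a comparison predicted to be significant, and the model-building claim itself omits attrition.

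It can also be said that the intent-to-treat set keeps every woman and that survival and mixed models use partial follow-up, so 210 is a crude count. That is fair, but it is the allowance the plan makes in its other power paragraphs, and H2b gives no reason to differ.

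Three stronger readings are tempting and not supported:

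- **That the plan claims 80% power for H2b at 250 women.** It attaches 80% only to N = 280, for the borrowed example's coverage criterion.
- **That a width of 0.40 is impossible or meaningless for relapse.** The plan does not state the scale of the width or the kind of interval, so nothing can be deduced about an implied standard deviation or about the N that relapse would need.
- **That H2b is underpowered.** At 300 women a 20-point difference, the size used for Aim 1, is detected with about 85% power even when the rule is cross-validated.

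**Conclusion.** The point holds as a wrong justification of modest severity. The 250 contains no relapse or PHQ-9 quantity from this trial and is not power for the H2b comparison, which has none stated. On its own criterion it is missed once the plan's 30% attrition is applied: 210 against 250, or 175 if the Extension women lack relapse interviews. These conclusions need only the plan's figures, plus, for the 175, an even spread of Extension women across the cells.

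The power figures rest on assumptions the plan does not make: 45% average relapse, equal groups, and binary relapse in place of time to relapse. They also treat the comparison as if AD continuation were randomised, when it is the woman's choice. They indicate scale: differences near 20 points are within reach, while 10 to 15 points are largely not at 210 women. The right word for the plan's claim is unsupported.

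**What to change.** In the H2b power paragraph:

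1. Apply the 30% attrition, giving about 210 analysable women, with 300 as the no-attrition case. Reconcile the Extension text with its measurement schedule, and use the resulting count of women with relapse data.
2. Describe the 250 as a precision heuristic for model building, borrowed from a time-to-pregnancy example. Remove or qualify the statement of sufficient power.
3. Add the minimum detectable relapse difference between indicated and contraindicated women at the expected analysable N, with the assumed rates and split written out.
4. Base that figure on out-of-sample recommendations and a calibrated test, such as a permutation test.
5. Give symptom burden its own statement on the PHQ-9 scale.

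The cost is one rewritten paragraph and a short simulation. No additional women, visits or change in conduct are required. The resulting power statement will be less favourable.

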In UPWARD, UPWARD Extension and UPWARD-S, if suicidality is endorsed with a score of greater than 1 on EPDS item #10 or PHQ-9 item #9 or on any of the self-report questionnaires (such as the SITBI or CCM), subjects will be prompted to complete the CS-S to assess risk of suicidality. Study subjects will also be given the national suicide [contact]) and informed that answers to online questionnaires are not monitored in real time. A positive score on questions 3, 4, or 5 on the CS-S, indicating intention or plan for suicidality, will prompt a safety call by study physicians. Suicidality expressed during the course of clinical or qualitative interviews, either through discussion, endorsement of the suicidality item on the MINI mood module, endorsement of items 3, 4, or 5 on the suicidality module of the MINI, or via scoring >2 on the MADRS item 10, will prompt study staff to complete the CS-S with the participant. A positive score on items 3, 4, or 5 of the CS-S administered by staff will also prompt a safety call by study physicians. In addition, subjects will be told by study staff to call their community providers and go to their nearest emergency room. Endorsement of items 3-5 on the CS-S prompting a physician safety call has been the threshold used in previous studies at the collaborating site (University of Colorado Boulder). As this is a community-based study with collaboration from community physicians, these providers dictate treatment. We will notify community providers directly via phone or fax within 24 hours from report of positive scores on CS-S items 3-5.

VI. BIOSTATISTICAL ANALYSIS

Preliminary Analyses: Differences between the MMB and UC in demographic characteristics and depression related characteristics (e.g., symptom severity, comorbidity) will be assessed using Chi-square test for binary variables, Cochran Mantel Haenszel tests for categorical variables, and t-tests for continuous variables. Variables that show significant group differences and predict outcome will be entered in analyses as covariates; AD exposure will be included as a covariate. All participants will be considered evaluable for analysis (intent-to-treat sample). Significance levels will be evaluated at $p < .05$, and effect sizes reported.

Analysis for Specific Aim #1: To test the relative risk for depressive relapse and reduction of symptom burden between women randomized to digital MMB or UC.

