To test target engagement, we will use the same HLM methods described above to compare differences between MMB and UC in change in the putative targets during the intervention period. To test target validation, we will use recent statistical developments that apply formal causal inference concepts to mediation analyses. Causal mediation approaches address violations of the assumption of sequential ignorability (e.g., no confounding/randomization of the mediator) that is required for unbiased estimates of the M (mediator) \rightarrow Y (outcome) relationship. Addressing the issue of sequential ignorability yields unbiased estimates of the natural direct effect (NDE = the non-mediated effect of reduction of depressive related outcomes) and the natural indirect effect (NIE = the component of the intervention that seems to proceed through the respective mechanisms), with Total Effect = NDE + NIE.²⁷ A high NIE indicates that the subsequent outcomes are mediated through time-lagged mechanisms improvements. We have experience implementing these models which fall under the classification of marginal structural models (MSM), principal stratification (PS), structural nested mean models (SNMM), and rank preserving models (RPM),²⁸⁻³⁰ which we will apply for each putative target individually. Sensitivity analyses will be implemented using approaches outlined by Ding and VanderWeele.³¹

Power Analysis for Specific Aim #1: To test the relative risk for depressive relapse and reduction of symptom burden between women randomized to digital MMB or UC.

For the analysis of rates of relapse, in our efficacy study of MBCT,³² pregnant women who received MBCT evidenced approximately 30% lower rate of relapse than UC. In estimating the difference in relapse rates between MMB and UC, accommodating the sample size required to address Aim 2, N = 600 participants is required for randomization. With N=600, we have 95.5% power to detect a 20% difference in relapse rates (which is smaller than what we observed in our efficacy study) and allowing for 30% attrition, which is higher than attrition in our efficacy study of MBCT with pregnant women (15%) and lower than attrition in our digital delivery of MBCT work (approximately 40%).

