For the continuous outcomes, using the method described by Ahn et al. to derive formulas for power estimation of linear mixed models,³³ power calculations can be made for repeated measures designs under specified assumptions. Based on a sample size of 300 per group, assuming 30% attrition for a total of 175 per arm randomized, with an alpha-level at 0.05 based on a 2-tailed test, assuming a within correlation of 0.5, we have power of 86.5% to detect an effect size of .25. Varying the effect size, we have 95.7%, 99.0%, and 99.8% power for effect sizes of 0.3, 0.35, and 0.4 respectively, which are much smaller than the d=0.70 effect size

observed in our efficacy study of MBCT with pregnant women,³⁴ indicating that we are sufficiently powered.

Power Analysis for Specific Aim #2: To explore the specific benefit of MMB relative to AD discontinuation and questions regarding personalization that are of strong interest to pregnant women and their healthcare providers.

H2a: Comparison of MMB to UC among women who discontinue AD: Anticipating balance across the 4 cells (randomized to MMB or UC; choice of discontinue AD or maintain AD), with approximately 300 participants across the two cells of interest, we have 82.8% power to detect a 23% difference in relapse rates with 30% attrition, which is smaller than what would be expected comparing the relapse rates among women who received MBCT (19%) in the [name] et al. study of MBCT with pregnant women³² to the rate of relapse among women who discontinued AD during pregnancy (66%) in the Cohen et al. prospective study¹⁰).

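### The PHQ-9 power paragraph turns 300 per group less 30% into 175 instead of 210, and the H2b sufficiency claim carries no attrition allowance although the other aims take off 30%

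*Combined protocol and SAP*

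**What the plan says.** All of this is in Section VI (Biostatistical Analysis), apart from the allocation of 300 women to each arm, which is in Section IV (Subject Enrollment).

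- **Aim 1, continuous outcomes.** The power paragraph starts from 300 per group, applies 30% attrition and arrives at 175 per arm. With two-sided alpha 0.05 and a within-person correlation of 0.5, it gives powers of 86.5%, 95.7%, 99.0% and 99.8% for effect sizes 0.25, 0.30, 0.35 and 0.40. It does not say how many repeated measures were assumed.
- **H2b, treatment selection algorithm.** From a published example needing 280 at an interval width of 0.38, the plan moves to a width of 0.40 and says "we estimate a sample size of 250 is needed with 9 terms". It projects 150 MMB women who discontinue antidepressants and 150 UC women who continue, and concludes: "thus, our randomized sample (N=600) should be sufficiently powered to build a model with up to 4 moderator variables". No attrition figure appears.
- **The other aims.** The Aim 1 relapse calculation allows for 30% and places that between 15% in the team's efficacy study and about 40% in its digital work. H2a reads "with approximately 300 participants across the two cells of interest, we have 82.8% power to detect a 23% difference in relapse rates with 30% attrition". Aim 3 says the sample "even with as much as 30% attrition is more than sufficient to test mediation with 80% power".
- **Analysis set.** "All participants will be considered evaluable for analysis (intent-to-treat sample").

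**The concern.** The 175 looks wrong on its face, and the PHQ-9 powers are attached to it. A reader cannot tell which sample size produced them.

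H2b raises a different issue. It contains no false sum, since 150 + 150 = 300 does exceed 250. But it compares a required number with a randomised number, while the other power statements in the section first allow for 30% loss. H2a is the closest comparison: its pool is the same size and it shares one cell with H2b, the MMB women who discontinue. What is at stake is whether the word sufficient is justified for the personalisation hypothesis at the attrition the plan itself adopts.

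**Working it through.** **1. PHQ-9 power paragraph**

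Inputs from that paragraph: 300 per group, 30% attrition, correlation 0.5, two-sided alpha 0.05.

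Retained per arm: 300 × (1 − 0.30) = **210**.

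Where 175 could come from: 250 × 0.70 = 175, or 1 − 175/300 = 41.7% attrition. Neither is stated.

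Reproducing the stated powers needs an assumption, because the plan compares change over time by a cited method that is not in the documents. I assume a time-averaged difference over *m* equally correlated measures:

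- variance factor f = (1 + (m − 1) × 0.5)/m
- power = Φ(d × √(n/(2f)) − 1.96)

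| n per arm | m | f | d = 0.25 | d = 0.30 | d = 0.35 | d = 0.40 |
|---|---|---|---|---|---|---|
| *Stated in the plan* | – | – | 86.5% | 95.7% | 99.0% | 99.8% |
| 175 | 6 | 0.583 | 86.5% | 95.7% | 99.0% | 99.8% |
| 300 | 1 | 1.000 | 86.5% | 95.7% | 99.0% | 99.8% |
| 210 | 2 | 0.750 | 84.1% | 94.4% | 98.5% | 99.7% |
| 210 | 3 | 0.667 | 88.1% | 96.5% | 99.3% | 99.9% |
| 210 | 6 | 0.583 | 91.8% | 98.1% | 99.7% | 99.97% |

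The first two computed rows agree because 175/0.583 = 300/1 = 300. For 210 per arm to give the same powers, f would have to be 210/300 = 0.70. That solves to m = 2.5, so no whole number of measures fits. The stated powers match two different bases, neither of them 210, and cannot show which was used.

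**2. H2b**

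Inputs: 250 needed; 0.5 × 300 + 0.5 × 300 = 300 projected; attrition of 15%, 30% and about 40% from the Aim 1 relapse paragraph.

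The plan's 250: if the required number scales with the inverse square of the width, 280 × (0.38/0.40)² = 252.7, close to 250. This is a single check under an assumption. It suggests that the step from 280 to 250 adds no attrition allowance. It cannot show whether the 280 already held one.

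Women remaining of 300, if 250 counts women with outcome data:

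| Attrition | Remaining | Against 250 |
|---|---|---|
| 15% | 300 × 0.85 = 255 | +2% |
| 30% | 300 × 0.70 = 210 | −16% |
| 40% | 300 × 0.60 = 180 | −28% |

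Break-even attrition: 1 − 250/300 = 16.7%.

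**The case against.** The best defence of H2b is that its basis is open. The 250 is adapted from an outside example, and the documents do not say whether it counts women randomised or women with complete outcomes. If it counts women randomised, 300 against 250 is the right comparison and nothing is short. The plan also keeps every participant evaluable and uses time-to-event and mixed models, so a woman lost late still contributes; 210 is a count of completers, not a measure of information. Finally, Aim 2 is worded as exploratory, and the H2b text is hedged, noting that no standard formula exists.

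Most of this stands, and it is why the point is conditional. It does not remove the inconsistency: the same all-evaluable rule covers the other aims, where the plan still allows for 30%, and no reason is given for treating H2b differently.

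On the PHQ-9, it can be said that the number of measures is available elsewhere: Table 1 marks the PHQ-9 at 16 time points and adds two-weekly administration. True, but the power paragraph does not say how many of these it assumed. With m = 16, 210 per arm gives about 94% at d = 0.25 under the formula used here, not the stated 86.5%.

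Four stronger readings are tempting, and the documents do not support them:

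- **That 175 shows Aim 1 to be underpowered.** The slip runs the other way: 210 is 20% more than 175 (210/175 = 1.20).
- **That 175 shows the calculation was made for a total of 500.** The powers fit 300 per arm with one measure equally well.
- **That H2b is 16% short and needs more women.** This assumes that 250 counts retained women and that those lost contribute nothing.
- **That the interval would widen by a known amount.** This needs the width to scale as 1/√n, which the plan does not state.

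**Conclusion.** The point holds in two parts of different strength.

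The 175 is an arithmetic error: the stated inputs give 210 per arm, and the four PHQ-9 powers do not follow from those inputs. It is harmless to the Aim 1 conclusion provided several repeated measures are used. Under the time-averaged assumption with correlation 0.5, 210 per arm gives 88% or more at d = 0.25 with three or more measures. With two measures it would be 84.1%, slightly below the stated figure, which is why the assumed number must be given.

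The H2b part is an omission, not a miscalculation. Sufficiency is asserted without the 30% allowance used for Aim 1, H2a and Aim 3. If 250 means women with outcome data, the claim holds at 15% attrition and fails at 30%, with break-even at 16.7%. This rests on the plan's own 50% projections and on treating women lost as contributing nothing. What is established is that the attrition basis is missing, so sufficiency is not shown at the plan's own planning figure; it is not established that H2b is too small.

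A reader may also want to subtract the 100 UPWARD Extension women, whom the text excludes from follow-up interviews. Table 2 nevertheless marks the MINI mood module for them at follow-up. That is a separate question about relapse data and needs its own reconciliation; it does not decide this point.

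**What to change.** **PHQ-9 power paragraph.** Replace 175 with 210 per arm, in line with the 300 per arm in Section IV. Recompute the four powers and state the number of repeated measures assumed. If another base was really used, state it and say why.

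**H2b.** Replace the sufficiency sentence with a conditional one, for example: *The two cells are expected to hold 300 randomised women. If 250 counts women with outcome data, the requirement is met only if attrition is at most 16.7%: 255 of 300 would remain at 15%, 210 at 30% and 180 at 40%. Women with partial follow-up may still contribute information.* Then say which count 250 refers to, and how H2b will use partial follow-up under the all-evaluable rule. Do not add interval widths obtained by 1/√n scaling.

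**Cost.** Text and one rerun of the PHQ-9 power calculation. The H2b statement becomes conditional on attrition. Nothing changes in design, randomisation or enrolment.

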Hypothesis 2b. Considering women randomized to MMB who discontinue AD and women randomized to UC who maintain AD, we predict that a treatment selection algorithm will identify which approach works best for whom (baseline characteristic profiles) and that women who receive the algorithm indicated approach will have superior outcomes to those who receive the algorithm contraindicated approach.

Aim 3: To test the extent to which digital MMB engages putative targets.

Hypothesis 3: We predict that women randomized to MMB will show significantly greater improvement in maladaptive cognitive processing (i.e., reduced rumination, increased mindfulness and self-compassion) than women randomized to UC and that these changes will mediate relapse prevention.

UPWARD Supplemental Arms

Objective: In the supplemental arms we will investigate the prevalence, severity, longitudinal course, correlates and predictors of suicidal ideation and behavior among women during pregnancy and the postpartum period (Arm 1a). We will also examine the safety, feasibility, and acceptability of enrolling pregnant women with suicidal ideation in our parent trial of MMB compared to usual care (Arm 2). Additionally, we will describe the resources for responding to suicidal risk that are available for pregnant and postpartum women in community settings and the experiences of healthcare providers who provide care to these women during such a critical time in their lives (Arm 1b). We will lastly use a cross-sectional design to describe the characteristics and correlates of suicidal ideation and behavior among pregnant women (Arm 1c).

Arm 1: We will characterize a real-world population of pregnant and postpartum women by describing the characteristics, correlates, course, and predictors of suicidal ideation and behavior using mixed-methods in the context of cross-sectional and longitudinal designs.

Aim 1a. Using a prospective longitudinal design, we will describe the characteristics, correlates, course, and predictors of suicidal ideation and behavior among pregnant and postpartum women using clinical and qualitative interviews, self-report instruments, behavioral task, and medical records from community providers (n = 125).

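### H2b builds the treatment selection model and tests it in the same trial sample with no stated out-of-sample step; evaluated that way, the test favours the indicated approach in about 35–42% of trials when there is nothing to find

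*Combined protocol and SAP*

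**What the plan says.** Hypothesis 2b (II. Specific Aims) predicts that an algorithm on baseline characteristics will identify which approach suits whom, and that "women who receive the algorithm indicated approach will have superior outcomes to those who receive the algorithm contraindicated approach". The two approaches are MMB with AD discontinued and UC with AD maintained. The H2b paragraph under Analysis for Specific Aim #2 (VI. Biostatistical Analysis) repeats the prediction as a significantly lower relapse risk and symptom burden, and speaks of women randomized to the indicated or contraindicated approach.

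The H2b paragraph under Power Analysis for Specific Aim #2 projects 150 women in each cell of interest and says the randomized sample "should be sufficiently powered to build a model with up to 4 moderator variables". It ties the number four to preliminary data and ends: "We will conduct PAI analysis with the SAS software procedure PROC QLEARN".

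The general rule under Preliminary Analyses is: "Significance levels will be evaluated at $p < .05$, and effect sizes reported".

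No section mentions a hold-out sample, cross-validation, bootstrap optimism correction, a permutation test or an external validation sample. Preliminary data are cited for the number of moderators, not for an algorithm that is already frozen.

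**The concern.** One sample is described, the model is built on it, and the hypothesis concerns women in it. Without a separate evaluation step, a woman's own outcome enters the fit that labels her treatment indicated or contraindicated. The fitted interactions follow chance patterns in the data, and the labels then sort women along those patterns. The contrast therefore leans towards H2b even when no baseline characteristic modifies anything.

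At stake is a significant result, with an effect size attached, for an algorithm about who fares better stopping or continuing AD. A reader would take it as evidence of treatment selection when it could be noise.

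**Working it through.** **The plan's own figure.** The power paragraph cites an example in which "they estimated a sample size of 280 was needed to yield 80% power for superior coverage with 9 terms", "with an interval width of 0.38", and changes the width to 0.40. With n proportional to 1/width²: 280 × (0.38/0.40)² = 280 × 0.9025 = 252.7, against 250 stated. The cells also reproduce: 600 × 0.5 × 0.5 = 150 each, 300 in total. Nine terms fit four moderators: 1 treatment + 4 main effects + 4 interactions. So 250 is a sizing for interval width; it does not size or validate an indicated-versus-contraindicated test.

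**Inputs for the simulation.**
- Level 0.05 (Preliminary Analyses), taken as two-sided. Sidedness is stated only for the Aim 1 continuous outcome: "with an alpha-level at 0.05 based on a 2-tailed test".
- n = 300, and 300 × 0.70 = 210. The 30% attrition is the H2a figure; H2b applies none.
- Relapse of 40%, with 20% and 60% as alternatives. These are assumptions. The plan's anchors in the H2a power paragraph are 19% and 66%.
- Four independent standard normal moderators (assumption).
- No treatment effect and no interaction.

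**Procedure.** Fit the nine-term model (logistic for relapse, linear for a continuous score). Take the sign of each woman's predicted difference as her recommendation. Then compare indicated with contraindicated women in the same data (4,000 runs per row).

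| Outcome | n | Significant, favouring indicated | Mean spurious gap |
|---|---|---|---|
| 40% relapse | 300 | 38.8% | 9.9 points |
| 40% relapse | 210 | 37.2% | 11.5 points |
| 20% relapse | 300 / 210 | 36.4% / 36.8% | 7.8 / 9.4 points |
| 60% relapse | 300 / 210 | 37.7% / 36.7% | 9.6 / 11.5 points |
| Continuous | 300 / 210 | 38.9% / 38.0% | 0.20 / 0.24 SD |

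Every rejection favours the indicated group. The benchmark for that one-direction count is 2.5%, so 38.8% is 38.8/2.5 = 15.5 times nominal; as a two-sided rejection rate it is 38.8/5 = 7.8 times. A separate simulation covering n = 175 (an assumed smaller size) to 300 gave 35–42%. Because the plan's relapse outcome is time to event, an exponential-model and log-rank version with 30% early censoring was also run: 39% at n = 210 and 36% at n = 300.

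**Fewer or selected moderators.** With one fixed moderator the rate is 12–14%; with two, 21%. If the four are picked in the same data from 10 or 11 candidates, it is about 72–73%. (Eleven measures are listed under Personalization Variables.)

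**Candidate remedies.**
- Build on half, test on the other half: 4.4–6.0% two-sided, 1.8–2.9% favouring indicated. This is valid, but leaves 300/2 = 150 women for building, below the plan's 250.
- Ten-fold cross-validation: the mean gap falls to about zero. An ordinary test on the pooled folds still rejects in 12–15% of trials two-sided, and 4.7–6.5% favour indicated (benchmark 2.5%). The folds share training data, so the ordinary standard error is wrong.
- Ten-fold cross-validation with treatment labels permuted through the whole procedure: this tests no effect of approach for anyone. With a plain main effect and no moderation, two simulations gave about 22% and 27% rejection at 30% v 40% relapse, and about 84% and 75% at 25% v 45% (assumed rates).
- Permuting moderator profiles within each approach group, which keeps the main effect: 4–6% at nominal 5%, checked only without prognostic moderators.

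The main-effect problem is also present in-sample: at 30% v 40% relapse with no interaction, the contrast is significant in 65% (n = 300) and 58% (n = 210) of trials.

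**The case against.** The strongest objection is that the documents never say in words that the same women serve both steps. They name a method and a software procedure, and whether either brings its own internal validation cannot be seen from the documents. That stands as a limit. The finding rests on one sample, a model built on it, a hypothesis about it and no validation step described. A validation step documented elsewhere would answer it. But the text as it reads leads to in-sample evaluation, and nothing in it would stop an analyst from doing exactly that.

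Second, Aim 2 is framed as exploratory. That is true and lowers the consequence, but H2b is still a directional prediction of a significant difference under a general 0.05 rule.

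Three stronger readings are tempting and should be resisted:
- *The error rate is about 72%.* This needs in-sample selection of the moderators. The plan neither states nor excludes that, and four may already be fixed from preliminary data. The 35–42% figure assumes fixed moderators.
- *Cross-validation alone restores 5%.* The 5–6% seen afterwards counts one direction only, where nominal is 2.5%.
- *The trial would put the rule into practice.* Nothing provides for this. The Usual Care paragraph and section VII leave AD decisions with the woman and her community prescriber.

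**Conclusion.** The concern holds in this form. H2b builds and, as the text reads, tests its algorithm in one sample of 150 + 150 women with no out-of-sample step. With four fixed moderators and nothing to find, that test favours the indicated approach in about 35–42% of trials, against a nominal 2.5%, with a spurious gap of about 10–12 points at n = 300 and 210 (40% relapse). The result changes little across 20–60% relapse, a continuous score and a time-to-event outcome. It assumes independent normal moderators, equal cells and two-sided 0.05. It does not touch Aim 1.

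A separate limit remains after any correction of optimism. AD status is the woman's own decision (Usual Care paragraph), so the two cells are not randomised groups, and out-of-sample evaluation does not remove that confounding.

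**What to change.** In the H2b paragraph under Analysis for Specific Aim #2, state that:

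1. Each woman's recommendation comes from a model fitted without her (ten-fold or leave-one-out cross-validation), with any moderator selection repeated inside each fold. Name the moderators if they are already fixed.
2. The in-sample contrast is descriptive only.
3. The claim of treatment selection rests on a test aimed at moderation. Either compare the cross-validated algorithm with a benchmark that assigns everyone the single approach that does better overall, or use a resampling reference distribution for the whole procedure that preserves the main effect of approach. Permuting moderator profiles within each approach group is one example; check its error rate with prognostic moderators before adopting it. Do not use an ordinary test on the pooled folds or free permutation of treatment labels.
4. AD status is chosen. Adjust the contrast for baseline predictors of that choice, and replace randomized with received where the analysis paragraph describes the indicated approach. Hypothesis 2b in the Specific Aims already speaks of receiving it.

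This needs revised analysis wording and more computing time, and no new data. The apparent benefit will be smaller than an in-sample analysis would show.
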